## 8. PROCEDURES

Figure 1 shows the proposed workflow through the trial. Following the informed consent, each participant is assigned a unique study number and baseline data will be collected before randomization. At this point the research nurse will briefly explain the procedure and familiarize the participant with the Visual Analogue Scale (VAS) system for dyspnea (Appendix I) and pain (Appendix II). Trial treatment will be delivered by means of either a pigtail chest tube (size 10-14 Fr) or PleurX® catheter at bedside after randomization. Outcome measures will be assessed daily until the chest tube is removed and at routine follow-up visits at approximately 14 days, 28 days and three months after the day of procedure as outpatients if the patient has been discharged. While the chest tube is in place, daily symptom assessment will be performed, and daily chest x-ray (PA and lateral when possible) and 24-hour drain output will be recorded (Appendix III) to determine if RSP has been achieved, or if further intervention is indicated.

RSP is defined as chest tube drainage less than 100 cc over the previous 24 hours and a chest x-ray showing similar or decreased pleural space opacification compared to the baseline chest x-ray done the day of pleurodesis (day 0).

Objective determination of the chest x-ray finding will be based on the formal Radiology report in the medical record. If necessary, the findings will be clarified by personal communication between study personnel and the Radiologist reading the film. The algorithm for chest tube and pleural space management after TSP is specified in Figure 2. If RSP is not achieved on day 3, then management will be determined using the algorithm based on the chest x-ray findings and pleural drainage, and may include continued observation, repeat cathflo activase, chest CT, insertion of additional pleural drainage tubes, and repeat TSP with or without cathflo activase. At all follow-up visits after the chest tube has been removed, assessment will include chest x-ray and completion of the VAS for pain and dyspnea.

[figure not shown]
Figure 1. Proposed Workflow of the Trial

Assessments/tasks at visits:

- ◆ VAS scores for pain and SOB
- ◆ Drained volumes in 24 hours if the chest tube is still in place
- ◆ Serum hemoglobin if the chest tube is place
- ◆ CxR (PA and lateral)
- ◆ CT scan, as justified by the PI

Figure 2: Chest Tube Management Algorithm

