## 8.2. Assessments/Tasks

Following consent, a baseline assessment will be undertaken pre-randomization by a member of the trial team and entered into the REDCap system hosted at Office of Human Research of MHS. The following data will be recorded prior to randomization:

1. Patient demographics and physical characteristics
2. Mode of presentation, current diagnosis, cause of effusions (if known).
3. Medical history and current medication.
4. Previous pleural interventions.
5. Symptoms, including pain and SOB according to a visual analog scale (VAS) (Appendix I, II).
6. Pleural fluid biochemical and cytological test results
7. Baseline hemoglobin (day of or day before TSP)
8. Baseline (day of or day before TSP) CxR and chest CT (if available) findings.

After randomization and TSP with or without cathflo activase, all patients will have daily follow-up until the chest tube is removed, and at 14 and 28 days, and three months after TSP. At all visits, the following data will be recorded:

1. VAS for chest pain and SOB will be documented (Appendix I, II).
2. CxR (PA and lateral preferred).
3. Drained pleural volumes in 24 hours (if the chest tube is still in place).
4. Serum hemoglobin (only for inpatient visits within three days of the pleurodesis procedure).
5. Repeat pleural interventions.
6. Chest CT scan, as justified by the principal investigator.

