## **9.0 STATISTICAL METHODS**

### **9.1. Primary and Secondary Outcome measures**

The primary outcome measure is the proportion of patients with successful pleurodesis at day 3 after administration of TSP. Successful pleurodesis is defined as “radiographically satisfactory pleurodesis” (RSP), as evidenced by 1) chest x-ray demonstrating similar or decreased amount of pleural fluid/opacification compared to day 0 (day pleurodesis is performed) and 2) drainage

of less than 100 ml of fluid over the preceding 24 hours. Chest x-ray results will be scored on a three-point scale (-1, 0, +1) based on comparison of pleural space opacification on the side of the TSP to baseline:

1. Worse (-1): Pleural space opacification is worse, suggesting residual undrained fluid or reaccumulation of loculated fluid.
2. Same (0): Pleural space opacification similar to baseline.
3. Better (+1): Pleural space opacification is better, suggesting less pleural fluid than at baseline.

The secondary outcome measures will include the following:

1. Proportion of patients with RSP at any time after TSP
2. Duration of chest tube drainage
3. Days to achieve RSP
4. Pain and dyspnea scores as assessed by a visual-analogue scale (on a scale from 0 to 100 mm, with a score of 0 indicating a complete absence of symptoms and a score of 100 maximum symptoms).
5. Proportion of patients requiring repeat pleurodesis
6. Proportion of patients requiring additional chest tube
7. Change in serum hemoglobin levels within three days of cathflo activase
8. Length of hospital stay (in days) after TSP.
9. All hospital costs associated with both treatment arms.

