## 9.2. Statistical Analysis Plan

Statistical summaries and analyses of data will be performed at MHS. Descriptive analysis will be performed for all data including means and standard derivation or medians for continuous variables and proportions for categorical variables. Comparison of outcomes between the two arms will be performed using t-test for numerical variables and Pearson  $\chi^2$ -test or Fisher's exact for categorical variables, and a one-sided p-value of 0.05 will be considered to be statistically significant.

The main analysis for primary outcome will be performed as per the intention-to-treat principle, and will include all the randomized participants with an observed outcome.(26) The primary outcome of the success rate of pleurodesis at day 3 will be analyzed using  $\chi^2$ -test. Time to symptomatic fluid recurrence following initial successful pleurodesis within 3 months follow-up period will be analyzed using a log-rank test. An interim analysis will be performed by the Memorial Healthcare System Quality and Safety Steering committee under [name] (currently officially the DSMB for MHS) after 50 patients are randomized in order to test for efficacy. The O'Brien-Fleming stopping rule will be used, which requires a P value of < 0.0088 (1-sided) for the primary outcome in order to stop at the interim analysis. The O'Brien-Fleming rule requires a P value of < 0.05 (1-sided) at the final analysis in order to declare a statistically significant difference in the primary outcome.(27) Analyses will be performed with the use of Prism 7.0 or SPSS 26 software.

Costs will be those related to study medications, initial hospital stay, and subsequent hospitalizations. All costs will be reported in US dollars and in 2020 prices. Cost data for both

arms will be obtained from MHS Strategic Financial Support Services. Outcomes will be measured in terms of probability of treatment success and/or complication, and utility of health states, which will be transformed to quality-adjusted life years (QALYs), calculated as the success rate of pleurodesis from each patient at day 3 after administration of TSP combined with pain and dyspnea scores.

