## 16.0 ATTACHMENTS

1. Appendix I-Visual assessment scale for dyspnea
2. Appendix II-Visual assessment scale for pain
3. Appendix III-Bedside pleural drainage record
4. Appendix IV-Study Datasheet
5. Appendix V-Genentech Investigator Initiated Study Safety Information

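### Section 9.2 builds QALYs from day-3 success and symptom VAS scores, with no preference weight and no time, so the result would not be a QALY

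*Combined protocol and SAP*

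**What the plan says.** The abstract (section 2.0) promises an incremental cost-effectiveness comparison from a static decision tree. Secondary hypothesis 9 in section 4.2 is that the combination is as cost-effective as talc slurry alone.

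The method is in the last paragraph of section 9.2. Costs cover study medication, the initial stay and later hospitalizations. For effects, the plan states: "Outcomes will be measured in terms of probability of treatment success and/or complication". It adds "utility of health states, which will be transformed to quality-adjusted life years (QALYs" and then gives the calculation: "calculated as the success rate of pleurodesis from each patient at day 3 after administration of TSP combined with pain and dyspnea scores".

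Section 9.1 defines the components. Success is RSP: a chest x-ray no worse than on day 0, together with drainage under 100 ml in the preceding 24 hours. Pain and dyspnea are scored from 0 to 100 mm, "with a score of 0 indicating a complete absence of symptoms and a score of 100 maximum symptoms". The economic entry in the list of secondary outcomes is "All hospital costs associated with both treatment arms"; QALYs are not listed there.

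On data collection, section 8.2 says that at each visit "VAS for chest pain and SOB will be documented". Section 8 says that after tube removal "assessment will include chest x-ray and completion of the VAS for pain and dyspnea".

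**The concern.** A QALY is a preference weight for a health state multiplied by the time spent in it. The stated calculation contains neither factor. If it were followed, the analysis would give an index made of an x-ray and drainage endpoint and two symptom scales, and would label it a QALY. Readers would take an incremental ratio on that index to be comparable with cost-per-QALY figures from elsewhere, and it would not be.

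The plan does not use the term cost per QALY, but the abstract, hypothesis 9 and section 9.2 together imply such a ratio. At stake is therefore the trial's cost-effectiveness claim. Because the combining rule is open, it could also be chosen after the results are known.

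**Working it through.** The documents give no QALY figure to reproduce, so the check compares the stated calculation with what a QALY from a decision tree requires.

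**Required form.** Expected QALYs per arm = sum over branches of [branch probability x sum over health states of (preference weight x years in state)].

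**Each term against the documents:**

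- *Branch probability.* Day-3 RSP can fill this role. Section 6.1 plans on about 60% with talc alone and 80% with the combination. There is no fault here.
- *Preference weight.* The only candidates in the stated calculation are the pain and dyspnea VAS (section 9.1). They measure symptom severity, higher is worse, and they are not anchored at death = 0 and full health = 1. No value set or mapping from VAS to utility is given.
- *Time.* Day 3 is a time of measurement, not a duration. The abstract gives three months of follow-up and section 8.1 calls three months a minimum, but neither enters the calculation. No horizon is stated for the tree.
- *Utility source.* Section 8.2 lists 8 baseline and 6 follow-up items, 8 + 6 = 14, and none is a preference-based measure. None of the 5 attachments in section 16.0 is titled as one. The content of "Appendix IV-Study Datasheet" and of Figures 1 and 2 is not shown, so an item there cannot be excluded.
- *Combining rule.* None is given. The VAS visit is also open: scores are taken daily while the tube is in place, then at 14 days, 28 days and three months.

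**Why the missing rule matters.** Take two simple rules, neither of which is in the plan, with success coded 0 or 1 and one VAS score V.

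- Rule A, success + V: moving from failure to success adds 1, the same as 1 mm of VAS, and worse symptoms raise the index.
- Rule B, success + (100 - V)/100: moving from failure to success adds 1, the same as 100 mm of VAS, and worse symptoms lower the index.

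The weight of success relative to symptoms differs by 100/1 = 100-fold, and the sign of the symptom term reverses. This shows only that the wording does not fix a result. It does not estimate the error.

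**Two readings of the sentence.** If the calculation defines the QALY, both the weight and the time are missing. If it defines the utility, which is then converted to QALYs, the weight is still symptom severity and the conversion over time is still not described. Both readings lead to the same conclusion.

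**The case against.** The strongest reply is that section 9.2 condenses a decision-tree analysis into one sentence. It lists the probability of success and the utility of health states as separate inputs. In a tree, success is a probability and need not be a preference weight. Utilities may come from outside the trial, so the absence of an instrument from the visit schedule proves little. A sentence that says utilities will be transformed does not exclude weighting by time. On this view the plan is brief rather than wrong.

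Much of this stands. RSP should not be faulted for failing to be a preference weight, and the list of data items is supporting evidence only. What does not stand is the defence of the payoff. The plan names utility but then says how the quantity is calculated, from each patient's own success and symptom scores. An analyst who followed that text would use neither a utility nor a duration.

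Three stronger readings are tempting and are not supported:

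- *That day-3 RSP is unsuitable as an effect measure.* It is a legitimate branch probability and a legitimate effect in natural units.
- *That the QALY gain would be overstated by a known factor.* With a three-month horizon, the planned difference 0.80 - 0.60 = 0.20 is worth at most 0.20 x 1 x 0.25 year = 0.05 QALY, so entering 0.20 directly would overstate it at least 4-fold. But no horizon is stated, and nothing says that 0.20 would be entered as QALYs or how the VAS scores would change it.
- *That no utility source exists.* The text available names none, but Appendix IV and the figures are not shown.

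**Conclusion.** The concern holds for the payoff side of the calculation. As written, section 9.2 would produce a quantity that is not a QALY. This is more than missing detail, because a calculation is stated and following it gives the wrong kind of quantity. No numerical size or direction can be attached to the error.

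The consequence is confined to the economic evaluation: a ratio on this index could not be interpreted as cost per QALY. The day-3 primary comparison, the 136-patient sample size and the hospital-cost comparison (objective 13 in section 4.2, outcome 9 in section 9.1) do not depend on it. The conclusion rests on the visible text. A utility source in Appendix IV would answer one part, but the stated calculation would still have to be changed to use it and to bring in time.

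**What to change.** In section 9.2:

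1. Delete the stated QALY calculation.
2. Use the probability of day-3 RSP as the effect in the decision tree, and keep complications as a model outcome. The section already lists both.
3. Report the cost difference per patient, the difference in day-3 RSP, and the incremental cost per additional patient with day-3 RSP = (mean cost, combination - mean cost, talc alone) / (RSP proportion, combination - RSP proportion, talc alone).
4. State one cost window, for example the three-month follow-up, since costs include later hospitalizations. Note beside the ratio that the effect is measured at day 3, so costs and effect cover different periods.
5. Report the pain and dyspnea VAS separately, outside the ratio.
6. Retain QALYs only if preference weights from a named source are applied to the health states and multiplied by time over a stated horizon.

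The change is to SAP wording and needs no new data. The cost is that the sponsor gives up the QALY label, and with it comparison with cost-per-QALY results elsewhere, unless it names a utility source and a horizon.

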## 10.0 STUDY ADMINISTRATION

### 10.1 Confidentiality and Privacy

Information about study subjects will be kept confidential and managed according to the requirements of the Health Insurance Portability and Accountability Act of 1996 (HIPAA). Those regulations require a signed subject authorization informing the subject of the following:

- What protected health information (PHI) will be collected from subjects in this study
- Who will have access to that information and why
- Who will use or disclose that information
- The rights of a research subject to revoke their authorization for use of their PHI.

This protocol and any amendments will be submitted to a properly constituted IRB, in agreement with local legal prescriptions, for formal approval of the study conduct. The IRB will be requested to grant approval of an authorization to collect the Protected Health Information with consent from subjects for research purposes. Prior to patient participation in the study, written informed consent will be obtained from each patient according to ICH GCP and to relevant MHS SOPs. Subjects may voluntarily withdraw from the program or revoke their authorization to share information related to the research. If a subject revokes authorization to collect or use PHI, the investigator, by regulation, retains the ability to use all information collected prior to the revocation of subject authorization.

Study data will be recorded and managed using REDCap (Research Electronic Data Capture) system hosted at Office of Human Research of MHS. No identifying information will be present on the REDCap. Instead, the data will be labeled by a unique study ID that will be linked to a separate master-code document that will be stored on a secure password-protected server. REDCap is a secure, web-based application designed to support data capture for research studies, providing 1) an intuitive interface for validated data entry; 2) audit trails for tracking data manipulation and export procedures; 3) automated export procedures for seamless data downloads to common statistical packages; and 4) procedures for importing data from external sources. The key linking data to PHIs will be destroyed by deleting the document five years after completion of the study.

### **10.3. Records Retention**

Study data will be recorded into the REDCap system hosted at Office of Human Research of MHS, and the trial database will be transferred securely to the principal investigator. All CxR and CT images relating to trial participation will be securely stored on MHS systems in line with routine clinical practice. Representative CxR and CT images will be stored on an encrypted trial hard drive. The study site will retain all records related to the study in accordance with MHS and ICH GCP guidelines in order to comply with applicable regulatory requirements.

## **11.0 ETHICAL CONSIDERATIONS**

### **11.1. Potential Risks to Subjects**

From the limited published data and our experience on clinical use of Talc and cathflo activase for pleurodesis, the treatment appears safe. The following are expected risks associated with the proposed interventions for this trial:

- Pain at drain site
- Bleeding
- Fever
- Allergic reaction to cathflo activase

Pain and fever are well-acknowledged risks of TSP and are not specific to the experimental intervention in this trial. Subjects may or may not have some or all of these risks from treatment with either one of the reagents used in this study. The risks for the use of talc with cathflo activase are the same as for standard of care with Talc alone except for an increased risk of bleeding and the possibility of an allergic reaction. Neither an allergic reaction nor clinically significant bleeding has been encountered with more than 300 doses so far administered in routine clinical practice at MHS.

Any adverse event that results in hospitalization or prolonged hospitalization will be documented and reported as a serious adverse event unless specifically instructed otherwise in this protocol. Details of any adverse events or serious adverse events will be collected during routine and trial follow-up visits. The clinical course of each event will be followed until resolution, stabilization, or until it has been determined that the study treatment or participation is not the cause. Serious adverse events that are still ongoing at the end of the study period must be followed up to determine the final outcome. All AEs and SAEs will be recorded in the patient's medical records and reported to the IRB.

In the event of a serious adverse event such as anaphylaxis, exsanguinating hemorrhage or death, the study code will be broken to determine if the subject received the study drug.

### **11.2 Safeguards to Minimize Risks**

This study will be conducted in compliance with the standards of good clinical practice. Participant safety will be ensured through regular review and follow-up. During the procedures, vital signs including blood pressure and oxygen saturation measurements will be used to ensure patient well-being. Hemodynamic measurements and serum hematocrit will be used to monitor for clinically significant pleural bleeding. Chest X-ray will be used to verify tube position.

### **11.3. Potential Benefits to Subjects**

There may be an immediate potential benefit to patients. The combination of talc with cathflo activase may increase successful pleurodesis rates and may also shorten the time of pleurodesis compared to talc alone, thus potentially improving patient symptoms and reducing the need for additional pleural interventions and hospital stay. Patient discomfort may also be reduced by earlier chest tube removal and shorter pleurodesis times.

### **11.4. Potential Benefits to Society**

If this trial is positive, it will directly improve future care for patients requiring pleurodesis for their symptomatic recurrent pleural effusion.

### **11.5. Subject Compensation**

There is no compensation for subjects participating in this study.

### **11.6. Risk/Benefit Assessment**

This study is to determine if intrapleural administration of cathflo activase improves the successful rates of TSP. The procedures used in the trial are the same as for standard care of pleurodesis with talc. The risks to patients participating in this trial are potential for loss of privacy, and that there may be an increased risk of bleeding with cathflo activase compared to talc alone. However, participants may benefit from the research if cathflo activase improves the efficacy of the TSP and/or the result. Based on our previous findings that intrapleural administration of cathflo activase improved drainage of these complex pleural effusions with no significant complications noted ([name], et al. unpublished data), it is possible that participants will benefit from this trial without increase in pleurodesis-related complications.

## **12.0 PUBLICATION PLAN**

The principal investigator and co-investigators of this study will be responsible for ensuring the results obtained from this study, regardless of the outcomes, will be reported to MHS's IRB within a reasonable timeframe after conclusion of the study. Results will be published in international and peer-reviewed scientific journals and presented at international conferences.

## 13.0 CONFLICTS OF INTEREST

There are no conflicts of interest by any investigator in this study.

## 14.0 FUNDING SOURCE

Genentech has agreed to support this trial through provision of the study drug (cathflo activase) at no cost and financial support for administrative expenses.

